# 6.3.3.2 PK Endpoints

To assess the PK of TAK-906 (at single and multiple oral doses up to 100 mg and 100 mg BID, respectively) in Japanese healthy male subjects, plasma and urine concentration of TAK-906 and its metabolite, M23 will be examined, and the following PK parameters for TAK-906 will be derived:

- Single dose period (Day 1):  $AUC_{\infty}$ ,  $AUC_t$ ,  $C_{max}$ ,  $t_{max}$ ,  $Ae_t$ ,  $f_{e,t}$ ,  $CL_R$
- Multiple dose period (Day 7): AUC $\tau$ ,ss, Cmax,ss, tmax,ss, Ae $\tau$ , fe, $\tau$ , CLR

Other PK parameters maybe calculated if deemed necessary for the interpretation of data.

# 6.3.3.3 PD Endpoints

The following PD parameters for serum prolactin will be derived:

- Single dose period (Day 1): AUCt, Cmax
- Multiple dose period (Day 7): AUCτ,ss, Cmax,ss

Other PD parameters maybe calculated if deemed necessary for the interpretation of data.

Serum prolactin levels will be measured as a target engagement marker. Dopamine inhibits prolactin production by pituitary lactotroph cells. When the  $D_2$  receptor is inhibited, serum prolactin levels rise and can serve as a marker for dopamine  $D_2$  receptor engagement.

# 6.3.4 Critical Procedures Based on Trial Objectives: Timing of Procedures

For this trial, the collection of blood samples for TAK-906 PK is the critical procedure.

- At any post-dose time point, the blood samples for TAK-906 PK need to be collected as close to the exact nominal time point as possible.
- All other procedures should be completed as close as possible, either before or after these prescribed/scheduled times.
- When ECG and/or vital signs measurements are scheduled at the same time as PK sampling, the blood draw will take priority and ECG and/or vital signs will be obtained within an acceptable time window (see Appendix C).
- The order of priority can be changed during the trial with joint agreement of the investigator and the Sponsor.
- Any nonscheduled procedures required for urgent evaluation of a safety concern will take precedence over all routine scheduled procedures.

# 6.4 Trial Design/Dosing/Procedures Modifications Permitted Within Protocol Parameters

Dose level in Cohort 2 may be changed within the range up to 100 mg, as appropriate, based on the safety and pharmacokinetic data of preceding cohorts, ie, 50 mg BID in Cohort 1 or 10 mg BID in Cohort 3 (if applicable) of this study.

# 6.5 Trial Beginning and End/Completion

# 6.5.1 Definition of Beginning of the Trial

The overall trial begins when the first subject signs the trial's informed consent form.

# 6.5.2 Definition of End of the Trial

The overall trial ends when the last subject completes the last planned or follow-up visit/interaction associated with a planned visit (this can be a phone contact), discontinues from the trial or is lost to follow-up (ie, the investigator is unable to contact the subject).

# 6.5.3 Definition of Trial Discontinuation

Trial discontinuation because of nonsafety reasons, such as:

- A finding (eg, PK, PD, efficacy, biologic targets) from another nonclinical or clinical trial using the trial treatment(s) results in the trial being stopped for a nonsafety-related reason.
- Data from comparator(s), drug(s) of the same class, or methodology(ies) used in this trial become available and results in the trial being stopped for a nonsafety-related reason.
- The trial is stopped because of nonscientific and nonsafety reasons, such as slow enrollment.

Trial discontinuation because of safety reasons:

• Early trial termination because of unanticipated concerns of safety to the trial subjects arising from clinical or preclinical trials with the trial treatment(s), comparator(s), drug(s) of the same class, or methodology(ies) used in this trial.

# 6.5.4 Criteria for Premature Termination or Suspension of the Trial

# 6.5.4.1 Criteria for Premature Termination or Suspension of the Trial

The study will be completed as planned unless 1 or more of the following criteria are satisfied that require temporary suspension or early termination of the study.

- 1. New information or other evaluation regarding the safety or efficacy of the study medication that indicates a change in the known risk/benefit profile for TAK-906, such that the risk is no longer acceptable for subjects participating in the study.
- 2. Significant violation of Good Clinical Practice (GCP) that compromises the ability to achieve the primary study objectives or compromises subject safety.
- 3. Two or more subjects in any single cohort or across more than 1 cohort experience any of the Takeda Medically Significant List events (as outlined in Table 10.a).
- 4. Two or more subjects in any single cohort experience a QTcF of >500 msec or an increased QTcF of >60 msec relative to baseline.
- 5. Abnormal liver function:

TAK-906	
Study ID TAK-906-1004	Page 24 of 71
Protocol	6 June 2017

- a. Two or more subjects in any single cohort or across more than 1 cohort experience alanine aminotransferase (ALT) and/or aspartate aminotransferase (AST) elevations of  $>5 \times$  upper limit of normal (ULN) in the absence of a concomitant bilirubin increase.
- b. One or more subjects in any single cohort experience ALT and/or AST elevations of >3 ×ULN in the presence of a total bilirubin increase of >2 ×ULN or an international normalized ratio (INR) of >1.5 without findings of cholestasis or other alternate etiology to explain the elevations (ie, "Hy's Law cases").
- c. Two or more subjects in any single cohort or across more than 1 cohort experience ALT and/or AST elevations of  $>3 \times ULN$  with the appearance of fatigue, nausea, vomiting, right upper quadrant pain or tenderness, fever, rash and/or eosinophilia (>5%).

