#### 6.2 Dose Escalation

The investigator will comprehensively examine the blinded safety results (AEs, physical examinations, vital signs, records of laboratory tests, and 12-lead ECG findings) obtained at all examinations by 14 days after the start of study drug administration in Cohort 1 and then determines the entry of Cohort 2 after discussion(s) with the Sponsor, and if appropriate, with medical experts.

Other criteria to consider discontinuation of the entry of Cohort 2 are as follows.

- 1. On an occasion that a SAE, of which relationship to the study drug cannot be denied, is observed.
- 2. At the onset of an AE for which relationship to the study drug cannot be denied and for which it is considered difficult to give medications continuously.

Furthermore, the maximum dose in this study was set at 100 mg BID for Cohort 2, based on the data from preceding studies, as described in Section 6.3.2. Dose level in Cohort 2 may be changed within the range up to 100 mg, as appropriate, based on the safety and pharmacokinetic data of preceding cohorts, ie, 50 mg BID in Cohort 1 or 10 mg BID in Cohort 3 (if applicable) of this study.

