# 6.5.4.2 Procedures for Premature Termination or Suspension of the Trial

In the event that the Sponsor, an IRB, or a regulatory authority elects to terminate or suspend the study or the participation of an investigational site, a study-specific procedure for early termination or suspension will be provided by the Sponsor; the procedure will be followed by applicable investigational sites during the course of termination or study suspension.

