## 10.2.9.3 Reporting SAEs

When an SAE occurs through the AE collection period it should be reported according to the procedure outlined below:

An SAE should be reported by the investigator or sub-investigator to the Sponsor (see Protocol Annex 1) within 1 business day of the first onset or notification of the SAE, along with any relevant information. The investigator should submit a detailed SAE Form to the Sponsor within 10 calendar days. The information should be completed as fully as possible but contain, at a minimum:

- A short description of the event and the reason why the event is categorized as serious.
- Subject identification number.
- Investigator's or sub-investigator's name.
- Name of the study medication(s).
- Causality assessment.

Any SAE spontaneously reported to the investigator or sub-investigator following the AE collection period should be reported to the Sponsor if considered related to study participation.

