## **17.0 APPENDICES**

#### Appendix A Responsibilities of the Investigator

- 1. Conduct the appropriate study in accordance with the protocol and GCP considering the rights, safety and wellbeing of human subjects.
- 2. When a part of the important activities related to the study are delegated to a sub-investigator or the study collaborator, prepare the lists of activities to be delegated and responsible personnel, submit the lists to the head of the investigational site in advance to get them accepted.
- 3. Prepare a written informed consent form and other written information, and update as appropriate.
- 4. Confirm the contents of the clinical study agreement.
- 5. Provide necessary information on the protocol, medications and responsibilities of individual personnel to the sub-investigator and study collaborator, and provide guidance and supervision.
- 6. Screen subjects who meet the requirements of the protocol, provide the explanation of the study in writing and obtain the written consent.
- 7. Assume responsibility for all the medical judgement related to the study.
- 8. Ensure in collaboration with the head of the investigational site that sufficient medical care for all clinically significant AEs related to the study are provided to subjects throughout and beyond the period when subjects participate in the study, upon obtaining consent from the subject.
- 9. If a subject consults other medical institution or other department, notify the physician of the medical institution or department of the subject's participation in the study, as well as the end and termination of the study in writing, and document such records.
- 10. In case of urgent report of a SAE, immediately notify the head of the investigational site and the Sponsor in writing.
- 11. Determine the need of emergency key code blinding of a subject in case of emergency.
- 12. Prepare correct and complete eCRFs, and submit them to the Sponsor with electronic signature.
- 13. Check and confirm the contents of eCRFs prepared by the sub-investigator or transcribed from the source data by the study collaborator, and submit them to the Sponsor with electronic signature.
- 14. Discuss any proposal from the Sponsor including update of the protocol.
- 15. Notify the head of the investigational site of the end of the study in writing.

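### Except for a Hy's Law case, no event-specific stopping criterion acts on one subject, so holding the other men's next dose after one possibly drug-related SAE is left to judgement

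*Protocol*

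**What the plan says.** Under protocol 6.5.4.1 the study runs to completion unless a listed criterion is met, and a criterion that is met requires suspension or termination. Item 1 is general: new safety or efficacy information that changes the risk/benefit profile "such that the risk is no longer acceptable for subjects participating in the study". Item 2 concerns GCP violations. The others are tied to named events. Item 3 is met when "Two or more subjects in any single cohort or across more than 1 cohort experience any of the Takeda Medically Significant List events". Items 4 (QTcF), 5a and 5c (transaminases) also need two subjects. Item 5b is the exception: "One or more subjects in any single cohort experience ALT and/or AST elevations of" more than 3 × ULN, with raised bilirubin or INR and no other explanation.

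Other sections bear on a single event:

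- 6.2 lists reasons to consider not opening Cohort 2. The first is: "On an occasion that a SAE, of which relationship to the study drug cannot be denied, is observed".
- 6.5.3 defines discontinuation for safety reasons: "Early trial termination because of unanticipated concerns of safety to the trial subjects arising from clinical or preclinical trials" or from related sources.
- 6.5.4.2 covers what happens when "the Sponsor, an IRB, or a regulatory authority elects to terminate or suspend the study".
- 12.2 lets the investigator depart from the protocol without prior agreement to remove an immediate hazard.
- 7.6 and 7.7 stop the affected subject.
- On reporting, Appendix A item 10 says: "In case of urgent report of a SAE, immediately notify the head of the investigational site and the Sponsor in writing". Section 10.2.9.3 requires a report to the Sponsor "within 1 business day of the first onset or notification of the SAE, along with any relevant information".

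**The concern.** The subjects are healthy men who can expect no benefit beyond examinations and health information, and clinical safety information comes from one foreign phase 1 trial (4.3). They are confined from Day -1 to Day 8 and dosed to a fixed clock. If one man has an SAE that may be due to the drug, the site should learn of it quickly, and someone must decide whether the other seven take their next dose. For liver injury the protocol settles this in advance: one Hy's Law case is enough. For any other possibly related SAE, death included, it does not. Two rules that look as if they might help do not: the SAE rules deal with reporting, and 6.2 deals with entry to Cohort 2. The same gap applies to Cohort 3, which runs in parallel with Cohort 1 or 2.

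**Working it through.** The documents give no operating characteristic for these rules and no event rates, so there is no figure to reproduce and no probability is claimed. The check is a reading of the rules plus a count of doses.

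**Step 1. Subjects needed for each event-specific criterion (6.5.4.1).**

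| Item | Event | Subjects needed |
|---|---|---|
| 3 | Event in Table 10.a | 2, within or across cohorts |
| 4 | QTcF above 500 msec or increase above 60 msec | 2, same cohort |
| 5a | ALT/AST above 5 × ULN | 2, within or across cohorts |
| 5b | Hy's Law | 1 |
| 5c | ALT/AST above 3 × ULN with symptoms or eosinophilia | 2, within or across cohorts |

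Four of five need two subjects. None names death or a related SAE as such.

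**Step 2. What one possibly related SAE sets in motion.**

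| Section | Who is covered | Mandatory hold for the other men? |
|---|---|---|
| 6.5.4.1 item 1 | Whole study | Binding, but only once the risk is judged unacceptable |
| 6.5.3, 6.5.4.2 | Whole study | No: permits or describes a stop |
| 12.2 | As the investigator decides | No: permits a deviation |
| 6.2 | Entry of Cohort 2 | No: a matter to consider, and not about men already dosing |
| 7.6, 7.7 | Affected man | No |
| 10.2.9.3, Appendix A item 10 | Reporting | No |

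Section 6.2 therefore gives no protection within a cohort, nor once Cohort 2 is dosing at up to 100 mg twice daily.

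**Step 3. Doses still scheduled.** Inputs: one dose on Day 1, two per day on Days 3 to 6, one on Day 7 (9.2.6); eight men per cohort, six on TAK-906 (6.1).

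Doses per man = 1 + 4 × 2 + 1 = 10. After k doses each man has 10 − k left. With all eight on the same study day, the other seven have 7 × (10 − k). If the affected man is on TAK-906, five of the seven are also on it, giving 5 × (10 − k).

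| SAE after | k | Left per man | Other seven | Five on TAK-906 | Next dose |
|---|---|---|---|---|---|
| Day 1 | 1 | 9 | 63 | 45 | about 48 h |
| Day 3 morning | 2 | 8 | 56 | 40 | about 12 h |
| Day 5 morning | 6 | 4 | 28 | 20 | about 12 h |
| Day 6 evening | 9 | 1 | 7 | 5 | about 12 h |
| Day 7 morning | 10 | 0 | 0 | 0 | none |

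After the single dose there is about 48 hours for review. From Day 3 there is about 12, and a reporting limit of one business day can be longer than that.

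**The case against.** **Item 1 already covers it.** A reader might infer that 6.5.4.1 obliges the study to carry on after a first related torsade de pointes, because item 3 needs a second case. The text does not support that. Item 1 has no subject count, binds once met, and can lead to a temporary suspension. In volunteers with no expected benefit, a related torsade or death is a plain candidate for it. This objection stands, and it limits the point: no power is missing. What remains is that item 1 needs a conclusion about risk first, whereas a hold is most useful while the case is still being reviewed. The proposed trigger also needs a judgement, on causality, but a narrower one.

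**This is not first-in-human dosing.** The foreign trial gave single doses of 5 to 300 mg and 50 and 100 mg twice daily for 5 days, with favourable safety and tolerability (6.3.2). Part of the design and dose rationale is redacted. This stands and lowers the urgency.

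**Single events are escalated in other ways.** Section 10.2.9.4 sends clinically significant QTc, neurologic and prolactin events to the Sponsor quickly, even when not serious. Section 6.2 also names a related AE that makes continued dosing difficult. Section 10.2.10 covers expedited reports on issues that might change dosing or conduct. Appendix A makes the investigator responsible for medical judgement. All true, but each is reporting or discretion.

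**The trigger is broad.** Related is defined widely (10.2.2), an SAE includes prolonged hospitalisation (10.1.1), and two of eight men receive placebo. A hold could follow an event that proves unimportant. This stands, and it is why the rule should be a temporary hold, not a stop.

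**Conclusion.** The point holds as a cheap improvement that should be made. It is not a contradiction in the protocol. Four of five event-specific criteria need two subjects, and after one possibly related SAE no stated rule holds the next dose for men already dosing.

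The dose counts (up to 56 after the Day 3 morning dose, 28 after the Day 5 morning dose) are what remains if nobody uses a discretionary route. They also assume that all eight men share a study day, which the documents do not state. With staggered starts the count could reach 7 × 10 = 70 if the affected man was dosed first, and the zero after Day 7 would not be assured. Men in a parallel cohort are not counted.

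A reader might also infer that a hold tied to SAEs would catch every syncope or extrapyramidal event, since these are monitored under 10.2.9.4 but not listed in Table 10.a. It would catch them only when serious.

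**What to change.** Add one item to 6.5.4.1:

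> After any one SAE, including death, whose relationship to study drug cannot be denied, further dosing is temporarily held in all open cohorts from the next scheduled dose. Dosing resumes only after the investigator and Sponsor have reviewed the case and the blinded safety data and documented the decision to resume, to lower the dose (Cohort 2 only, per 6.4), or to terminate.

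Leave items 3 to 5 unchanged. A death clearly unrelated to study drug does not trigger the hold. Section 6.4 ties a Cohort 2 dose change to data from preceding cohorts, so if a reduction partway through Cohort 2 is intended, 6.4 should say so.

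Two matching changes are needed:

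- **SAP.** The significant deviations listed in 7.2 are entry criteria only, so men with interrupted dosing could stay in the Day 7 steady-state summaries unless judged not evaluable. State that men who missed doses because of a hold are left out of the Day 7 PK and PD summaries.
- **Protocol 7.8.** Replacement now applies to a subject who discontinues. Extend it to men whose dosing was interrupted by a hold.

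No new data are needed: causality is defined in 10.2.2 and is already a minimum element of the SAE report (10.2.9.3). The costs are possible loss of some Day 7 profiles, from only six active subjects per dose, and the chance that an event in a man on placebo triggers a hold.

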# 7.6 Criteria for Discontinuation or Withdrawal of a Subject

Primary reasons for discontinuation or withdrawal of a subject from the study or study drug should be recorded in the eCRF using the following categories. For subject failure, refer to Section 7.5.

1. Death. The subject died on study.

Note: If the subject dies on study, the event will be considered as SAE. See Section 10.2.9.3 for the reporting procedures.

2. AE. The subject has experienced an AE that requires early termination because continued participation imposes an unacceptable risk to the subject's health or the subject is unwilling to continue because of the AE.

In multidose studies, study drug should be discontinued immediately with appropriate clinical follow-up (including repeat laboratory tests, until the subject's laboratory profile has returned to normal/baseline status, see Section 9.2.8), if the following circumstances occur at any time during study drug treatment:

- Liver Function Test (LFT) Abnormalities
  - ALT or AST >8×ULN, or
  - ALT or AST >5×ULN and persists for more than 2 weeks, or

- ALT or AST >3×ULN in conjunction with elevated total bilirubin >2×ULN or INR >1.5, or
- ALT or AST >3×ULN with appearance of fatigue, nausea, vomiting, right upper quadrant pain or tenderness, fever, rash and/or eosinophilia (>5%).
- QT prolongation
  - QTcF >500 msec or  $\Delta$ QTcF (change from baseline in QTcF) >60 msec.
- 3. Protocol deviation. The discovery post-dose that the subject failed to meet protocol entry criteria or did not adhere to protocol requirements, and continued participation poses an unacceptable risk to the subject's health.
- 4. Lost to follow-up. The subject did not return to the clinic and attempts to contact the subject were unsuccessful. Attempts to contact the subject must be documented in the subject's source documentation.
- 5. Withdrawal by subject. The subject wishes to withdraw from the study. The reason for withdrawal, if provided, should be recorded in the eCRF.

Note: All attempts should be made to determine the underlying reason for the withdrawal and, where possible, the primary underlying reason should be recorded (ie, withdrawal due to an AE should not be recorded in the "voluntary withdrawal" category).

- 6. Study terminated by the Sponsor. The Sponsor terminates the study.
- 7. Other

Note: The specific reasons should be recorded in the "specify" field of the eCRF.

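### Suspension criterion 5a excludes ALT/AST >5×ULN cases with a bilirubin increase of unstated size, so on two of three readings a mild bilirubin rise takes a subject out of the count

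*Protocol*

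**What the plan says.** Protocol 6.5.4.1 lists conditions and states that the study runs as planned unless one or more "criteria are satisfied that require temporary suspension or early termination of the study". Item 5 covers the liver:

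- **5a:** two or more subjects, in one cohort or across cohorts, with ALT and/or AST >5×ULN "in the absence of a concomitant bilirubin increase".
- **5b:** one or more subjects with ALT and/or AST >3×ULN "in the presence of a total bilirubin increase of >2 ×ULN" or INR >1.5, "without findings of cholestasis or other alternate etiology to explain the elevations".
- **5c:** two or more subjects with ALT and/or AST >3×ULN plus a listed symptom, fever, rash or eosinophilia >5%.

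Criterion 5b gives its bilirubin increase a size. Criterion 4, on QTcF, gives its increase both a size (>60 msec) and a reference (baseline). Criterion 5a gives neither, and no section of the protocol or SAP defines the term.

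Protocol 7.6 sets separate rules for stopping study drug in an individual, "if the following circumstances occur at any time during study drug treatment". One limb reads "ALT or AST >3×ULN in conjunction with elevated total bilirubin >2×ULN or INR >1.5, or"; it has no exception for an explained rise. Exclusion criterion 25 (Protocol 7.2) bars bilirubin only above 1.5×ULN, so a subject may enter with a value above ULN.

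**The concern.** A transaminase elevation accompanied by rising bilirubin is, if anything, more worrying than the same elevation alone. A rule that counts the second and drops the first orders hepatic risk the wrong way. Whether 5a does this depends on one undefined word. *Increase* can mean above ULN, above the subject's baseline, or above 2×ULN as in 5b, and these give different counts for the same data.

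At stake is whether a second case triggers a criterion that the protocol describes as requiring action. The subjects are healthy volunteers with no therapeutic benefit, and earlier clinical safety data come from one foreign phase 1 trial (Protocol 4.3). A numeric stop should give every reader the same answer.

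**Working it through.** The plan states no figure to reproduce: the sample size is not based on power, and neither document gives a hepatic event rate. The check is logical.

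**Inputs** (Protocol 6.5.4.1). T = the higher of ALT and AST; B = total bilirubin; B0 = baseline bilirubin, all in multiples of ULN. E = cholestasis or another cause found. F = a 5c feature present.

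- 5a: T > 5 and no bilirubin increase
- 5b: T > 3 and (B > 2 or INR > 1.5) and not E
- 5c: T > 3 and F

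Three readings of *increase*: R1, B > 1; R2, B > B0; R3, B > 2. The >1×ULN boundary in R1 is an assumption of this check; it appears nowhere in 5a to 5c.

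**Step 1: one subject.** T = 6, INR = 1.0, no 5c feature.

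| B (baseline B0) | E | 5a, R1 | 5a, R2 | 5a, R3 | 5a, phrase deleted | 5b |
|---|---|---|---|---|---|---|
| 0.9 (0.9) | no | yes | yes | yes | yes | no |
| 1.5 (0.8) | no | no | no | yes | yes | no |
| 1.5 (1.5) | no | no | yes | yes | yes | no |
| 2.5 (at most 1.5) | no | no | no | no | yes | yes |
| 2.5 (at most 1.5) | yes | no | no | no | yes | no |

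Row 2 is the main gap: not counted under R1 or R2, counted under R3. Row 3 shows that a stable value at the entry limit is not an increase under R2. Conversely, under R2 a rise within the normal range, such as 0.8 to 0.9, would remove a subject. Row 5 is the second gap and holds on all three readings. Because entry is limited to 1.5×ULN, a later value above 2×ULN is a rise from baseline as well as above ULN.

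**Step 2: grid.** T > 5, no 5c feature; B (≤1, >1 to 2, >2) × INR (≤1.5, >1.5) × E (no, yes) = 3 × 2 × 2 = 12 combinations. Those counted by none of 5a to 5c:

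- R1: B >1 to 2 with INR ≤1.5 (2), B >1 to 2 with INR >1.5 and E (1), B >2 with E (2). Total 2 + 1 + 2 = 5.
- R3: B >2 with E only. Total 2.
- Phrase deleted: 0.

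R2 cannot be placed on this grid without baselines. The combinations are not weighted by likelihood, so 5, 2 and 0 describe coverage, not risk.

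**Step 3: the two-subject count.** Subject A has ALT 6×ULN with bilirubin 0.9×ULN, unchanged from baseline. Subject B has ALT 6×ULN.

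| Subject B's bilirubin | R1 | R2 | R3 | Phrase deleted |
|---|---|---|---|---|
| 1.5×ULN, baseline 0.8 | 1 | 1 | 2 | 2 |
| 1.5×ULN, baseline 1.5 | 1 | 2 | 2 | 2 |
| 2.5×ULN with cholestasis | 1 | 1 | 1 | 2 |

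Criterion 5a needs 2.

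**Step 4: individual stop (Protocol 7.6).** ALT/AST >8×ULN stops dosing whatever the bilirubin. At >5 to 8×ULN with bilirubin not above 2×ULN, INR ≤1.5 and no listed feature, the only other numeric limb is "ALT or AST >5×ULN and persists for more than 2 weeks, or" the limbs that follow. From first dose on Day 1 to last dose on Day 7 is 7 − 1 = 6 days, so that limb cannot be met during dosing. Row 5 of Step 1 does stop the individual, through the bilirubin limb of 7.6, yet does not count at trial level.

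**The case against.** **Context supplies the threshold.** 5a and 5b sit in one list, use the same noun and set absence against presence. The bilirubin limit paired with transaminases is >2×ULN in 5b, in 7.6 and in the abnormal-LFT reporting rule (10.2.9.5). On that reading the main gap disappears. This is a reasonable view of the intent and it stands as a possibility. But 5a refers to none of those places, and a required stop should not rest on inference.

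**The second gap may be deliberate.** 5b looks for unexplained cases, and stopping an individual without asking the cause while the trial-level rule looks for an unexplained signal can be coherent. That explains 5b. It does not explain 5a, which has no etiology exception when bilirubin is normal: an explained ALT of 6×ULN counts there.

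**Other protections remain.** Cohort 2 entry needs a full blinded review of Cohort 1 safety data, with two single-event triggers to consider not proceeding: a possibly related SAE, or a possibly related AE that makes continued dosing difficult (6.2). Criterion 1 of 6.5.4.1, the general AE limb of 7.6 and the >8×ULN individual stop also apply. ALT/AST >3×ULN calls for repeat liver tests including bilirubin and INR within 7 days, preferably 48 to 72 hours (9.2.8.1). Chemistry falls on Days 2, 5, 8 and 14 and the last dose is on Day 7, so of the scheduled post-dose results only Days 2 and 5 can stop dosing within a cohort. All this stands and makes the effect small. None of it is a numeric trial-level stop for these cases, and the 6.2 review gates Cohort 2 only; Cohort 3 runs in parallel.

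**Stronger readings that the documents do not support.** A reader might infer that 5a as written certainly drops every subject with bilirubin >1 to 2×ULN; it does so only under R1, and under R2 only if the value has risen. A reader might also infer that such subjects are unprotected; the safeguards above show otherwise. Finally, a reader might take 6.5.4.2, "In the event that the Sponsor, an IRB, or a regulatory authority elects to terminate or suspend the study", to make the criteria optional. That section describes procedure once a decision is made, and 6.5.5.2 repeats the wording for sites.

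**Conclusion.** The point holds as a defect of wording with a small practical effect; confidence is moderate. 5a leaves its bilirubin condition undefined. On the above-ULN and above-baseline readings, a bilirubin rise not exceeding 2×ULN removes a subject with ALT/AST >5×ULN, INR ≤1.5 and no 5c feature from all of 5a to 5c. On the >2×ULN reading it does not. The second gap, bilirubin risen above 2×ULN with cholestasis or another cause and no 5c feature, exists on all three readings.

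This assumes that the etiology exception in 5b applies to both its bilirubin and its INR limb, and that entry bilirubin is at most 1.5×ULN. No claim is made about how often such cases would occur.

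**What to change.** Preferably delete the bilirubin phrase from 5a, so that ALT/AST >5×ULN in two or more subjects counts whatever the bilirubin; this closes both gaps. At minimum, replace it with *without total bilirubin >2×ULN*, which settles the reading and closes the main gap only.

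Either is a change to one phrase. No new tests are needed: ALT, AST and total bilirubin are already in the chemistry panel on Days 2, 5, 8 and 14. The downside is that a few more cases may count towards suspension, and under deletion some of them would have an explained bilirubin rise.
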